11.0 Specimen Collection and Banking (if applicable)

Specimens (i.e. blood samples) will be collected at the laboratories at MUSC or the Ralph H. Johnson VA Medical Center

- Blood samples will be collected at each visit
- The specimens will be labeled with a code that only study personnel can link back to a study subject. Researchers outside of this study will not be given a link between the code number and name or any other identifying information. Other information might include race, ethnicity, sex, medical history. Such information might be important for research or public health. It is possible that this information (including genetic information) might come to be associated with your racial or ethnic group.
- Specimen will be stored in the laboratory freezers with limited access; all associated data will be stored in the password protected server that can be accessed only by research personnel at MUSC. Blood samples obtained at MUSC will be stored in a locked minus 80°degree freezer in the Clinical Science building 927 while those obtained at the VAMC will be stored in the locked minus 80°degree freezer in the Strom Thurmond building 411.
- The blood samples and cells will be destroyed at the end of 10 years.
- Research personnel (PI, program study coordinator, graduate student, post-doctoral scholar, and a technician will) have access to specimen and associated data

- Research personnel (PI, program study coordinator, graduate student, post-doctoral scholar, and a technician will) will be responsible for receipt or transmission of the data or specimens.
- No specimens or associated data be sent to an outside facility

Specimen/Banking for Future Use

- If blood samples are used in future unrelated studies, prior approval will be obtained from the MUSC Institutional Review Board. This future research may be conducted by [name] or by other researchers who obtain IRB approval for their research.
- The specimens will be labeled with a code that only study personnel can link back to a study subject. Researchers outside of this study will not be given a link between the code number and name or any other identifying information. Other information might include race, ethnicity, sex, medical history. Such information might be important for research or public health. It is possible that this information (including genetic information) might come to be associated with your racial or ethnic group.
- The blood samples and cells will be destroyed at the end of 10 years.
- Only study personnel will have access to specimens
- This research will not involve genetic studies.
- Study participants may request at any time that their research samples be removed from storage and not be used for future research. Study participants may contact [name] via written communication at the following address: : [name] Once the request is received, and if the samples have not already been used for other research, they will be destroyed. If this request is not made, the specimens will be stored indefinitely or until completely used.

[figure not shown]
12.0 Data Management

Statistical Analysis Plan and Sample Size Justification for Aims 1 and 2

The primary outcomes in Aim 1 are serum antibody levels and functional antibody response measured using the OPA response at baseline and 30 days post-PVC₁₃ vaccine measured in the five groups defined in Table 1. The primary outcomes in Aim 2 are absolute number and proportion of B-cells phenotype specific to PPS₁₄, 19A, and 23F at baseline and 7 days post-PVC₁₃ vaccine measured in the same five groups. Comparisons between groups and within group between times for each aim will be evaluated using a linear

mixed model (LMM) approach. **The models will include fixed effects for participant group (65-75 RT, 35-45 RT, 65-75 DM/HTN, 65-75 healthy, and 35-45 healthy) and for time (day 0 or 30) and a random subject effect to account for repeated measures of antibody levels within participant.** Model assumptions will be checked graphically and transformations will be considered when necessary. Comparisons for each outcome between groups and within group between times will be evaluated using a series of contrasts from the LMM. **We are presenting power calculations for a range of assumptions to demonstrate that we anticipate having sufficient power to detect observed differences for all comparisons even if we fail to meet the recruitment target.** For power calculations we estimated the effect sizes for sample sizes ranging between 10 to 40 participants per group measured at 2 times at 80% and 90% power using a two-sided test assuming within subject correlation of 0.5 and Bonferroni adjusted and unadjusted significance

Figure 7: Effect sizes for different sample sizes, power, and significance

levels of $p = 0.005$ and 0.05 respectively. We will also evaluate the correlation between serum antibody levels and B cell count with OPA response across all participant groups using an LMM approach where OPA response is the dependent variable and antibody level or B-cell count is the independent variable. The model will include a random subject effect to account for repeated measures in the same subject. We anticipate good correlation (between 0.6-0.99), thus the objective is to estimate the correlation and define the level of precision around that correlation. A sample size of 200 subjects, 40 per group, provides >80% power to detect weak correlations of $r = 0.20$ and allows us to estimate a 95% confidence interval around the correlation to within ± 0.14 .

Statistical Analysis Plan and Sample Size Justification for Aim 3

Aim 3 will examine differences in expression of TNFR markers (TACI, BCMA, and BAFF-R) using single cell qPCR on a subset of 10 participants (5 responders and 5 non-responders) from each of the 5 groups described in Aims 1 and 2 evaluated at baseline and 7 days post-vaccination. Single cell qPCR allows us to not only evaluate differences in expression between groups but also allows us to estimate the within subject and within group heterogeneity with great precision. Each participant sample provides between 40-96 viable cells that will be evaluated for gene expression at the single cell level. Relative fold-change in expression between participants who are 65-75 RT, 35-45 RT, or 65-75 DM/HTN with respect to the relevant controls will be evaluated using a linear mixed model approach. The model will include fixed effects for participant group, response status, and time and a random subject effect to account for repeated measurements resulting from individual cells from the same subject samples. Comparisons of number of gene expression between groups and within group between times will be evaluated using a series of contrasts from the LMM. For comparisons within group between responders and non-responders, a sample size of 5 responders and 5 non-responders with ≥ 40 cell level measures at 2 time points provides 80% power to detect 2.7 fold-increase or a 0.60 fold-decrease in expression using a two-sided test assuming within subject correlation of 0.5 and a Bonferroni corrected significance level (up to 10 comparisons) of $p = 0.005$. For comparisons between groups, we will have 10 subjects per group allowing us to detect even smaller fold-changes in expression.

All electronic data will be kept on the VA secure V drive or R drive and on MUSC secure Z drive that only team members will have access to.

13.0 Provisions to Monitor the Data to Ensure the Safety of Subjects (if applicable)

All adverse events (AE) will be reported and monitored through the data safety monitoring plan. The AE's will be characterized by: intensity/severity; expectedness; relatedness; frequency; outcome; treatment or action taken.

Monitoring will be performed at each study visit by the study coordinator and/or P.I. and will occur at the Ralph H. Johnson VA Medical Center and MUSC and all AEs will be recorded on an event form with physician/nurses/coordinator notes attached. These will be reviewed by the safety monitoring committee. The safety monitoring committee will include board certified Infectious Diseases specialists. Meetings will occur on a quarterly basis. [name], the P.I. will arrange for the meetings quarterly, make all materials available for review by the committee and be ultimately responsible for the meetings.

The study endpoints will be reporting and assessing safety of the vaccination and blood draw procedures and to ensure that these procedures are well within the acceptable complication risk associated with vaccination and blood draws.

All serious, unexpected, AND related adverse events will be reported to the MUSC IRB within 10 working days of learning of the event.

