We will measure TNFR expression by B cells following immunization with PCV13 in 65-75 year old RT and compare them to each of the groups described in Specific Aim 1. Gene expression, with focus on the B cell activating factor (BAFF) system, will be measured in PPS-specific and non-PPS specific B cells using single cell genomics and flow cytometry. These measures will be correlated with post-immunization functional antibody activity, a surrogate of protection.

Our central hypothesis is that the aging RT population responds poorly to PCV13 vaccination reflecting the combined effects of aging and RT. We postulate that both the number of memory B cells and expression of tumor necrosis factor (TNF) superfamily receptors, which play crucial roles in the response to pneumococcal polysaccharides (PPS), are deficient in the elderly RT population and contribute to poor pneumococcal vaccine responses.

We have developed fluorescently labeled PPS allowing us to study the nature and surface receptors of PPS-specific B cells. Our preliminary data demonstrate that RT recipients 1. Respond poorly to pneumococcal immunization as measured by antibody titer and functional antibody activity. 2. RT recipients and healthy elderly have lower absolute number of both IgM and switched memory B cells. 3. The number of PPS-specific IgM and switched memory B cells are significantly lower in RT recipients and 4. TACI and BAFF-R, members of the TNF superfamily receptors, expression is significantly lower in the PPS-specific memory B cells in the RT population versus healthy controls. The overall objective of this proposal is to characterize the immune response and explore possible mechanisms of poor vaccine responsiveness following immunization with PCV in the rapidly growing group of elderly with RT. As the RT population is a

heterogeneous group we will study only those in whom the underlying cause of renal failure is diabetes mellitus type 2 (DM2) and/or hypertension (HTN).

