We have developed directly labeled fluorescent PPS to enumerate and characterize PPS-specific B cells. This allowed the analysis of antigen-specific B cell responses to pneumococcal vaccination. The results of these studies demonstrated that the immune response to PPV in young adults consists predominantly of IgM memory B cells [16]. In contrast, in the elderly who are deficient in memory B cells, particularly IgM memory B cells [17], the predominant B cell phenotype in response to PPS consists of switched memory B cells (IgG/A+IgM-CD27+)[18]. HIV+ individuals, are also deficient in CD27+IgM+ B cells yet the predominant response consists of PPS-specific CD27+IgM+ B cells [19-22], albeit at significantly reduced numbers. Thus, the cause of poor pneumococcal vaccine responses varies according to study population. Several investigators and our preliminary data show that like the elderly and HIV-positive, absolute number and percentage of memory B cells are significantly lower in stable RT recipients, at 6 months to 5 years post-RT, compared to healthy subjects [23, 24]. Moreover, low number and percentage of IgM memory B cells correlate with poor antibody responses to PPV23.

This may however not be the only cause for poor vaccine responses. The ability to isolate antigen-specific B cells allows us to explore other deficits and/or changes in surface markers and gene expression potentially implicated in poor vaccine responses. It has been well described that members of the TNFR family and

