3. Known anaphylaxis, hypersensitivity or “bad allergic reaction” to the pneumonia vaccine. This does not include egg allergy or previous Guillan Barre syndrome.
4. Those who received blood products or gamma globulin within 3 months.
5. Inability to comprehend or sign the informed consent form
7. Previous/present illness that may affect immune response to the vaccine (previous pneumococcal Disease, removal of the spleen, auto-immune disease such as lupus or rheumatoid arthritis, end-stage liver disease, or cancer)
8. Significant abnormalities (3xULN and all those considered to be critical values) in CBC, chemistries including glucose.
9. HIV, HBsAg or HCV positivity
10. Receipt of PPV23 within 1 year

Groups 1 (65-75 yrs) and 2 (35-45 yrs) Renal Transplant populations

Inclusion Criteria:

Age range; RT 35-45 or 65-75 years old,
 End stage renal disease cause either DM2 and/or hypertension (HTN)
 Renal transplant >12 months ago
 We will not restrict volunteers with respect to gender, ethnic or racial group.

Exclusion criteria:

1. Medications that are known to affect immune function (chemotherapy, anti-TNF α agents) with the exception of anti-rejection medication.
 2. Episode of acute rejection within the last 6 month period
- The inclusion/exclusion criteria will be determined by chart review and pregnancy test for females of child bearing potential.

Group 3: Diabetic/hypertensive 65-75 year old controls

Inclusion Criteria

65-75 years old with DM2 and/or HTN.
 Previous immunization with PPV23 >1 year prior
 Willingness to be tested for HIV, HBV and HCV
 “normal kidney function” defined as glomerular filtration rate (GFR) of 60% or above
 We will not restrict volunteers with respect to gender, ethnic, or racial group.

Exclusion Criteria

1. Medications that are known to affect immune function (chemotherapy, anti-TNF α agents).

The inclusion/exclusion criteria will be determined by chart review.

Group 4: Healthy Control 65-75 yr old

Inclusion Criteria

65-75 years old without DM2. May have high blood pressure (systolic>140 and/or diastolic>90) as long as it is well controlled (systolic<140 and/or diastolic <90) and has not affected kidney function.
 Previous receipt of PPV23 > 1 year prior
 Willingness to be tested for HIV, HBV and HCV
 We will not restrict volunteers with respect to gender, ethnic, or racial group.

Exclusion Criteria

6. Medications that are known to affect immune function (chemotherapy, anti-TNF α agents).

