10.0 Study Design / Methods

The overall objective of this proposal is to characterize the immune response and explore possible mechanisms of poor vaccine responsiveness following immunization with PCV in the rapidly growing group of elderly with RT. As the RT population is a heterogeneous group we will study only those in whom the underlying cause of renal failure is diabetes mellitus type 2 (DM2) and/or hypertension (HTN). There will be 5 study groups as outlined above.

Volunteers from all 5 study groups will be recruited as above. All individuals from study groups 1-4 who meet the study criteria will receive Prevnar13[®] on day 0. Group 5 volunteers will be recruited during the first year of the study and those who have not previously received PPV23 will receive PPV23 on day 0 and PCV13 on day 366. Blood samples will be obtained as outlined below and results obtained in various groups will be compared.

Timing of blood samples

Peripheral blood samples will be collected at day 0 (pre-immune), day 7, and day 30 (4 weeks post-PPV23) for groups 1-4 and at days 366, 373 and 396 for group 5. In addition, day 5, and 10 blood samples will be obtained from a limited (n=10) number of elderly RT participants to determine the optimal time point for circulation of PPS-specific B cells. Yearly blood samples will be obtained thereafter for serum antibody and OPA analyses to test longevity of antibody and OPA responses. Samples from days 0, 30 and yearly samples will be used for antibody titers and opsonophagocytic assays. Samples from day 0 (day of vaccination with PCV13) and day 7 will be used for flow cytometric analysis. The day 7 time point for isolation of antigen-specific B cells was specifically chosen as we have extensively studied temporal dynamics of antigen-specific B cell in peripheral blood samples (unpublished studies) and have found that the highest number of antigen-specific B cells are present in the peripheral circulation at day 6 and 7 with rapid (70+%) decline at day 8 in healthy young, elderly including those with DM2 and HTN, and HIV-positive. At day 30, a minimal number of PPS-specific B cells were present. Others have described similar findings [28, 29].

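### The mixed model listed for Aims 1 and 2 has no group-by-time term, so it cannot test whether the groups respond differently to PCV13

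*Combined protocol and SAP*

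**What the plan says.** Section 12.0 (Aims 1 and 2) specifies a linear mixed model: "The models will include fixed effects for participant group (65-75 RT, 35-45 RT, 65-75 DM/HTN, 65-75 healthy, and 35-45 healthy) and for time", with time given as day 0 or 30, and a random subject effect. It then says: "Comparisons for each outcome between groups and within group between times will be evaluated using a series of contrasts from the LMM". Transformations are allowed for, but no interaction, change-score outcome or baseline covariate is listed there or elsewhere.

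The question the model has to answer is set in section 1.0: "Our central hypothesis is that the aging RT population responds poorly to PCV13 vaccination reflecting the combined effects of aging and RT". Section 4.0 likewise frames the primary endpoint as what vaccination induces.

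For Aim 3, section 12.0 says: "The model will include fixed effects for participant group, response status, and time and a random subject effect". This is again main effects only, although the comparison it powers numerically is inside each group: "For comparisons within group between responders and non-responders, a sample size of 5 responders and 5 non-responders".

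**The concern.** A hypothesis that one group responds worse than another is about a difference between groups in change from day 0. A model with only main effects of group and time fixes that difference at zero. A random subject effect does not help, because it absorbs each person's level and not a group-specific change.

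The group contrast that remains mixes baseline and response. It can be significant because of a baseline difference alone, and it carries only half of a true response difference. The groups are not randomised, so nothing balances their baselines, and the document gives reasons to expect imbalance:

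- Section 2.0 reports that "absolute number and percentage of memory B cells are significantly lower in stable RT recipients".
- Prior PPV23 timing differs. In Group 5, "those who have not previously received PPV23 will receive PPV23 on day 0 and PCV13 on day 366", whereas the Group 3 criterion is open-ended ("Previous immunization with PPV23 >1 year prior"), and Group 4 has an equivalent one.

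**Working it through.** **The plan's own figures.** Five groups give 10 pairwise comparisons, and 0.05/10 = 0.005, the stated Bonferroni level. The one Aims 1-2 power figure given in the text is for a correlation of 0.20 with 200 subjects. It reproduces: Φ(atanh(0.20) × √197 − 1.960) = 81%, with a confidence half-width of about 0.139 at r = 0. It does not bear on the group contrasts. The effect sizes for those are in Figure 7, which is not available here.

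**Parameter count.** Five groups at two times have 10 cell means. Group plus time uses 1 + 4 + 1 = 6 fixed-effect parameters; adding group-by-time gives 10. Under the 6-parameter model, the contrast (change in Group 1) − (change in Group 5) has all coefficients equal to zero. This does not depend on any assumed effect.

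**What the group contrast estimates.** Let the baseline difference be b and the difference in change be d. The difference is b at day 0 and b + d after vaccination. With balanced data the additive contrast is the average, (b + b + d)/2 = b + d/2.

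**Size.** Inputs: the plan's correlation of 0.5, two-sided 0.05 and 0.005, and up to 40 per group (section 12.0); 275 subjects (section 6.0), so 275/5 = 55 per group. The SD of 1 at each time and the effect sizes are assumptions for illustration.

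- SD of change = √(2(1 − 0.5)) = 1. SD of a subject's mean over two times = √((1 + 0.5)/2) = 0.866.
- At n = 40, the SE of the difference in change = √(2/40) = 0.2236. The SE of the additive contrast = 0.866 × 0.2236 = 0.1936.
- Equal baselines, d = 0.8, interaction: 0.8/0.2236 = 3.578. Power = Φ(3.578 − 1.960) = 95%, or Φ(3.578 − 2.807) = 78%.
- Same case, additive: the estimate is 0.4, and 0.4/0.1936 = 2.066. Power = Φ(2.066 − 1.960) = 54%, or Φ(2.066 − 2.807) = 23%.

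| n per group | Additive, 0.05 | Interaction, 0.05 | Additive, 0.005 | Interaction, 0.005 |
|---|---|---|---|---|
| 20 | 31% | 72% | 9% | 39% |
| 40 | 54% | 95% | 23% | 78% |
| 55 | 68% | 99% | 35% | 92% |

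- Baseline gap only (d = 0), n = 40: the additive contrast estimates b. It is significant in 54% (0.05) or 23% (0.005) of studies for b = 0.4, and in 18% or 4% for b = 0.2. The interaction contrast rejects at its nominal 5% or 0.5%.
- Baseline 0.4 SD higher with a 0.8 SD response deficit: 0.4 − 0.8/2 = 0, so the deficit disappears.

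A simulation of five groups of 40 (20,000 runs) agrees. For the 0.8 SD deficit, power was 53.5% and 22.1% additive, against 94.4% and 76.6% interaction. For the 0.4 SD baseline gap, rejection was 53.6% and 22.4%, against 4.9% and 0.6%.

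**Within-group contrast.** Suppose Group 1 has no response and the others change by 0.5, 0.7, 0.8 and 1.3 SD. The shared change is 3.3/5 = 0.66 SD. In 4,000 simulated studies (n = 40, level 0.005) the listed model called the Group 1 change significant every time, against 0.8% with group-by-time.

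**Aim 3.** With 5 + 5 subjects in each of five groups and equal cell numbers, a 2.7-fold responder difference present in one group only is averaged over five: exp(ln 2.7/5) = 1.22-fold, reported for every group.

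**The case against.** The strongest reply is that this is a wording omission. The section twice promises comparisons over time inside each group, which cannot be delivered without an interaction, and the term list is not declared exhaustive. That is plausible, and Figure 7 might have shown the intent. But the model sentence is specific, and an analyst who follows it fits a model that cannot answer the question. Leaving it open also leaves the choice between two different questions until after the data are seen.

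Other points stand in part:

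- A significant contrast caused by a baseline gap reflects a real difference in level. It is an error only when read as a difference in response, which is how the hypothesis and endpoint are framed.
- The evidence for unequal baselines is indirect. The section 2.0 statement concerns memory B cells in general, not antibody. The PPV23 timing separates Group 5 from Groups 3 and 4, not Group 1 from Groups 2 or 3. The structural defect does not depend on this evidence.
- A day-30 difference adjusted for baseline is an alternative and can answer a different question in non-randomised groups. Difference in change follows more directly from the plan's model, which treats baseline as an outcome.
- Ten between-group and five within-group contrasts exceed the 10 that 0.005 covers. That tension is already in the plan.
- For Aim 3, group-by-response-status is enough for the powered comparison. It does not let the responder difference vary over time.

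**Conclusion.** The plan is wrong as written and should be corrected before analysis. The listed model forces one shared response, makes the promised within-group contrasts identical across groups, and cannot separate a response difference from a baseline difference. These results follow from the model terms alone, with balanced data needed only for the exact form b + d/2.

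The cost in power and in misleading significance depends on the illustrative effect sizes, SD 1 and the plan's correlation of 0.5. It is large wherever the response deficit or baseline gap is a moderate fraction of an SD. Whether the authors meant to include an interaction cannot be determined from the document.

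**What to change.** In section 12.0, Aims 1 and 2:

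- List the fixed effects as group, time and group-by-time.
- Define time as day 0 and day 30 for Aim 1, and as day 0 and the post-vaccination flow cytometry sample for Aim 2. Count from PCV13, so that day 366 is day 0 in Group 5.
- Name the between-group differences in change as the between-group contrasts, including Group 1 vs 2 and Group 1 vs 3, and take the within-group changes from the same model.
- Keep the stated 0.005 level.
- State which contrast the Figure 7 effect sizes describe.

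In Aim 3, add group-by-time and group-by-response-status.

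Cost: no new data, four extra fixed-effect parameters in each Aims 1-2 model, and eight in Aim 3 (four per interaction). At 40 per group, 80% power and the 0.005 level, the detectable difference in change is (2.807 + 0.842) × 0.2236 = 0.82 SD, under the same SD and correlation assumptions. If Figure 7 was computed for a different contrast, the sample-size text needs restating as well.

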The inclusion/exclusion criteria will be determined by chart review and pregnancy test for females of child bearing potential.

We will not restrict volunteers with respect to gender, ethnic, or racial group.

Group 5: Healthy Control 35-45 yr old

Inclusion Criteria

35-45 years old without DM2. May have high blood pressure (systolic>140 and/or diastolic>90) as long as it is well controlled (systolic<140 and/or diastolic <90) and has not affected kidney function.

Willingness to be tested for HIV, HBV and HCV and filling out a medical questionnaire that will include diabetes screening.

We will not restrict volunteers with respect to gender, ethnic, or racial group.

Exclusion Criteria

6. Medications that are known to affect immune function (chemotherapy, anti-TNF α agents).

The inclusion/exclusion criteria will be determined by chart review and pregnancy test for females of child bearing potential.

Diversity: we will attempt to mimic the local renal transplant recipient population consisting of a disproportionately high number of males (>60%) of African-American decent, \pm 50%. This gender and race pattern of distribution is consistent with the patient population of the Ralph H. Johnson VA Medical Center outpatient clinics, where we will be recruiting most of our control populations (Groups 3-5). We therefore anticipate a diverse population as a result of eligibility at the recruitment sites.

Children will NOT be included in this study as this study is uniquely aimed at defining the immune response to PCV13 in ADULTS. The immune response to PCV13 is age-dependent and therefore completely different in children, as is the recommended vaccine frequency.

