8.0 Recruitment Methods

- Potential study participants will be recruited from Ralph H. Johnson Veterans Affairs Medical Center and Medical University of South Carolina during the appointment with their treating physician. Flyers will be posted in the waiting room areas of the clinics and attending physicians and clinic nurses will be asked to keep this study in mind and mention availability of these studies to their patients when ordering PCV13 for them.
- Potential study subjects will be explained the purpose of the study and how their information was obtained (from a treating physician or a chart review); further the eligibility criteria will be explained and what involves in participating in the study: procedures, estimated time of commitment, any reasonably foreseeable risks, benefits, and compensation. In a similar manner, healthy volunteers will be recruited through flyer advertisement on MUSC campus as well as in VA.
- Potential study subjects will be identified by reviewing medical records and by physician's recommendations.
- Flyers will be used to recruit study subjects as well as broadcast emails for MUSC and VA employees and volunteers.

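### The groups are neither randomised nor matched and the Aim 1 and 2 model has no sex or race term, so any imbalance that affects levels would enter the between-group level contrasts

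*Combined protocol and SAP*

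**What the plan says.** Section 12.0 (Aims 1 and 2) gives the model as follows: "The models will include fixed effects for participant group", with the five groups listed, "and for time (day 0 or 30) and a random subject effect to account for repeated measures of antibody levels within participant". Comparisons between groups, and between times within a group, "will be evaluated using a series of contrasts from the LMM". No sex, race or other baseline term appears, and no sensitivity analysis is described. The Aim 3 paragraph does name an additional term: "The model will include fixed effects for participant group, response status, and time and a random subject effect". It has no demographic term either.

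Section 5.0 deals with sex and race through recruitment. It says "we will attempt to mimic the local renal transplant recipient population", described as more than 60% male and about 50% African-American. It adds that this pattern agrees with that of the VA outpatient clinics, "where we will be recruiting most of our control populations (Groups 3-5". There is no quota or matching, and the criteria for each group say that enrolment is not restricted by sex, ethnicity or race.

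The recruitment sources differ by group:

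- Groups 1 and 2 come from the MUSC and VA transplant clinics (section 5.0).
- Group 3 comes from VA internal medicine or endocrinology clinics (section 5.0).
- Healthy volunteers are sought by flyers on the MUSC campus and in the VA, and section 8.0 adds "broadcast emails for MUSC and VA employees and volunteers". Section 9.0 confirms that employees may be enrolled and are approached by mass email.

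The list of data to be collected in section 10.0 contains neither sex nor race. Section 11.0 mentions them only as information that might accompany stored specimens.

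**The concern.** Aim 1 sets out to separate the effect of age from that of transplantation by comparing groups. Nothing in the design balances those groups on other characteristics, so a difference in sex or race mix that also affects the outcome would be read as an effect of age or transplant. A random subject effect handles the correlation between repeated measures. It does not remove confounding between groups.

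Section 5.0 itself treats the sex and race mix as worth controlling, but the analysis has no fallback if the recruitment attempt falls short. The reason it gives for expecting similarity concerns clinic outpatients. Employees and campus volunteers are not an outpatient population, so that reason fits the healthy volunteers least well, and Group 5 in particular.

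**Working it through.** **1. The plan's own figures.** The effect sizes for group comparisons are in Figure 7, which is not available in the text. The other figures reproduce and are not in dispute.

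- Adjusted level: five groups give 10 pairwise comparisons, and 0.05/10 = 0.005, as stated.
- Power for r = 0.20 with 200 subjects (Fisher z, two-sided 0.05): atanh(0.20) × sqrt(197) − 1.96 = 0.886, and Φ(0.886) = 81.2%, consistent with the stated >80%.
- Half-width of the 95% interval at r = 0: tanh(1.96/sqrt(197)) = 0.139, consistent with ±0.14.

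**2. Which contrasts are exposed.** Write an outcome as group effect + time effect + β × (sex or race indicator) + subject effect + error, and leave the indicator out of the model.

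- *Between-group level contrast:* biased by Δp × β, where Δp is the difference between the groups in the proportion with the characteristic. The model as written has no group-by-time term, so its group contrast is of this kind.
- *Within-group contrast over time:* the same people are measured twice, so β cancels.
- *Between-group contrast of change:* β cancels here too with complete data, unless the characteristic modifies the response to vaccination.

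**3. Inputs for the size.** From section 12.0: 40 per group, two-sided levels of 0.05 and 0.005, and a calculation "assuming within subject correlation of 0.5 and Bonferroni adjusted and unadjusted significance" levels. Assumed, because the documents give neither: Δp of 0.10 to 0.30, and β of 0.2 to 0.5 SD.

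**4. Bias.** Lowest: 0.10 × 0.2 = 0.02 SD. Midpoint: 0.20 × 0.35 = 0.07 SD. Highest: 0.30 × 0.5 = 0.15 SD. This is per factor.

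**5. False-positive rate.** For a single time point, SE = sqrt(2/40) = 0.224 SD. A contrast of change has the same SE, because its variance factor is 2 × (1 − 0.5) = 1. The rate is P(|Z + bias/SE| > critical value), with critical values 1.960 and 2.807.

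| Bias (SD) | Shift = bias/SE | Nominal 5% | Nominal 0.5% |
|---|---|---|---|
| 0 | 0 | 5.0% | 0.50% |
| 0.02 | 0.09 | 5.1% | 0.52% |
| 0.07 | 0.31 | 6.1% | 0.72% |
| 0.15 | 0.67 | 10.3% | 1.7% |

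If the contrast averages both times, as the model without an interaction implies, the variance factor is (1 + 0.5)/2 = 0.75 and SE = sqrt(2 × 0.75/40) = 0.194 SD. A bias of 0.15 SD then gives about 12% and 2.1%.

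**6. Scale.** The detectable difference at 80% power on the single-time SE is (1.960 + 0.842) × 0.224 = 0.63 SD, or (2.807 + 0.842) × 0.224 = 0.82 SD at the adjusted level.

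**7. Precision cost of adjusting.** For one binary term and two equal groups, R² = ((p2 − p1)/4)² / (0.25 × p(1 − p)), where p is the mean proportion, and the contrast variance is multiplied by 1/(1 − R²). Assumed splits of 60% v 60%, 60% v 80% and 60% v 90% give 1.00, 1.05 and 1.14.

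**The case against.** The strongest reply is that no imbalance is shown. Section 5.0 expects similar sex and race mixes, names Groups 3-5 when it says so, and sets out to mimic the transplant population. Flyers and emails also reach the VA. With balance the bias is zero. Nor do the documents say that sex or race affects antibody, OPA or B-cell outcomes. All of this stands. A reader might infer that the sources are known to differ, or that section 5.0 overlooks Group 5. The documents support neither. They support only that similarity is hoped for, is not enforced, and is doubtful for volunteers who are not clinic patients.

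A second reply is that the aims concern response to vaccine, and that sex and race main effects leave complete-data contrasts of change untouched. That is correct and limits the point to level contrasts. It does not remove the point, because the group contrast of the model as written is a level contrast.

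Third, the model sentence may be only a summary. The plan promises time contrasts within each group, which need an interaction that it does not list, so one should not infer that covariates have been ruled out. Even so, the Aim 3 paragraph names its extra term, and no section names sex or race.

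Finally, a reader might expect adjustment to improve precision. That is not assured. Under imbalance, the added term costs a little.

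**Conclusion.** The point holds as a conditional and modest one. If sex or race differs between groups and affects the measured levels, the planned between-group level contrasts would carry that difference unadjusted. Within-group time contrasts would not, and contrasts of change would only if sex or race modifies the response.

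The size rests wholly on the assumed inputs. A bias of 0.02-0.15 SD is small beside a detectable difference of 0.63-0.82 SD. The false-positive rate runs from about 5.1% to 10% at nominal 5%, and from 0.52% to 1.7% at nominal 0.5%, on the single-time or change-contrast SE. It would be tempting to cite 10% as the error rate of this study. That figure needs both assumptions at their upper end; the midpoint gives about 6%. The change is worth making because it is cheap and because covariates chosen after the data are seen carry less weight. It is a refinement, and the plan is not unsound without it.

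**What to change.** - Add sex and race to the list of data to be collected in section 10.0, and report both by group.
- In section 12.0, pre-specify sex and race as fixed effects in the Aim 1 and Aim 2 mixed models, with the coding of race fixed in advance. Report the adjusted between-group contrasts beside the unadjusted ones.
- If contrasts of change are also to be adjusted, include the interactions of sex and race with time; main effects alone will not alter those contrasts.

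Sex and race are not consequences of age group or transplant, so adjusting for them removes none of the effect under study. The cost is two more recorded items, a few degrees of freedom out of 200 subjects, and a possible small loss of precision: a contrast variance factor of about 1.00-1.14 for one binary term under the assumed splits.
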